After subjects have been randomized, they will undergo brain connectivity imaging. We will obtain BOLD functional MRI in 30 patients with refractory MTLE during the task-free resting state. We will systematically determine for each patient the neocortical foci that are highly correlated and anticorrelated to the epileptogenic MTL by using a population-based map of normal resting-state MTL connectivity as a seed network of interest. This will allow us to selectively identify regions of relevant correlation to the MTL that fall within easily accessible areas for rTMS based on our technical experience (including most of the frontal, parietal, and lateral temporal cortex, while avoiding the frontopolar and occipital regions due to head positioning and the need for eyeglasses worn to calibrate the TMS neuronavigation system). **Subject time: 1 hour.**

2. Baseline seizure diary (12 weeks)

Subjects will keep a baseline seizure diary for 12 weeks, during which time connectivity analyses and tMS target creation will be performed by the investigators. **Subject time: 12 weeks.**

3. Pre-rTMS EEG (One hour to complete, on one day)

EEG recording of interictal epileptiform discharge (IED) frequency will occur prior to first TMS session. **Subject time: 1 hour.**

4. Experimental Design for rTMS (On average one and a half hours to complete, on ten consecutive weekdays)

We will conduct a controlled assessment of two different rTMS protocols applied to specific cortical targets (derived from connectivity imaging results) in the 30 patients with medically refractory MTLE. The cohort had been randomized into three treatment groups. In Group 1, we will target continuous low-frequency rTMS to cortical regions that are highly correlated with the epileptogenic MTL. In Group 2, we will target high-frequency rTMS to cortical regions that are highly anti-correlated with the epileptogenic MTL. Group 3 will receive sham TMS as a control intervention. Each subject will have ten 30 minute rTMS sessions over a two-week period, ten consecutive weekdays. **Subject time: 1.5 hours per rTMS session. 10 rTMS sessions.**

5. Post-rTMS EEG (One hour to complete, on one day)

EEG recording of interictal epileptiform discharge (IED) frequency will occur after the last TMS session. **Subject time: 1 hour.**

6. Follow-up seizure diary (12 weeks)

Subjects will keep a follow-up seizure diary for 12 weeks post rTMS. **Subject time: 12 weeks.**

7. Final EEG (One hour to complete, on one day)

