EEG recording of interictal epileptiform discharge (IED) frequency will occur 12 weeks after the last rTMS session. **Subject time: 1 hour.**

At 12-week follow-up, the primary outcome measure will be seizure frequency compared to baseline, and the secondary outcome measure will be IED frequency compared to baseline. Subjects will be blinded to their group assignment, as will the investigator who reviews seizure diaries and determines IED frequency on EEG. Adverse events will be tracked closely throughout the study protocol.

Follow-Up

The investigators will conduct a controlled assessment of the response to the initially chosen rTMS protocol and determine if the subject may be appropriate for further rTMS. Investigators may invite subjects back to repeat the study procedures 2-7. The follow-up rTMS protocol chosen by investigators will depend on the subject's response, or lack thereof, to the previously performed protocol.

Subjects who are invited back for further rTMS sessions and choose to return will undergo the following specific procedures:

1. Baseline seizure diary (12 weeks)

Subjects will keep a baseline seizure diary for 12 weeks, during which time connectivity analyses and tMS target creation will be performed by the investigators. **Subject time: 12 weeks.**

2. Pre-rTMS EEG (One hour to complete, on one day)

EEG recording of interictal epileptiform discharge (IED) frequency will occur prior to first TMS session. **Subject time: 1 hour.**

3. Experimental Design for rTMS (On average one and a half hours to complete, on ten consecutive weekdays)

Based on analyses of the subject's response to the initially assigned rTMS protocol, the alternative protocol (either low-frequency rTMS to cortical regions that are highly correlated with the epileptogenic MTL or high-frequency rTMS to cortical regions that are highly anti-correlated with the epileptogenic MTL) will be used. Each subject will have ten 30 minute rTMS sessions over a two-week period, ten consecutive weekdays. **Subject time: 1.5 hours per rTMS session. 10 rTMS sessions.**

4. Post-rTMS EEG (One hour to complete, on one day)

EEG recording of interictal epileptiform discharge (IED) frequency will occur after the last TMS session. **Subject time: 1 hour.**

5. Follow-up seizure diary (12 weeks)

Subjects will keep a follow-up seizure diary for 12 weeks post rTMS. **Subject time: 12 weeks.**

6. Final EEG (One hour to complete, on one day)

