Our expected statistical analyses will be based on intention to treat and will include an analysis of variance (ANOVA) with the factors Group (low-frequency vs. high-frequency vs. sham) and Time (baseline vs. follow-up) with repeated measures on time, to assess both seizure frequency (primary outcome) and IED frequency (secondary outcome). If indicated, post hoc analyses, corrected for multiple comparisons using the Bonferroni method, will be performed. Based on results from the two most directly relevant rTMS epilepsy studies in the literature^{5,4}, we estimate the effect size of a potential decrease in mean seizure frequency at 56%. To achieve 80% power, with a statistical threshold of $\alpha < 0.05$ and three equal treatment groups, the total sample size needed would be 27 subjects¹², so we plan to enroll 30 subjects.

According to the Epilepsy Foundation, temporal lobe epilepsy accounts for approximately 60% of all patients with epilepsy and MTLE accounts for 80% of all patients with temporal lobe epilepsy. MTLE is the most common form of refractory epilepsy in the patient population at BIDMC. At BIDMC, there are more than 3500 outpatient epilepsy visits annually with refractory epilepsy accounting for an estimated 1166 of those patients. Accordingly, we would estimate approximately 560 MTLE outpatient visits annually, likely representing more than 140 unique MTLE patients. Therefore, even accounting for refractory MTLE patients who are not eligible or who decline to participate, we anticipate that we would be able to recruit and enroll 30 subjects over the projected multi-year time period of this study.

Data Analysis.

We will obtain BOLD functional MRI in 30 patients with refractory MTLE during the task-free resting state. We will systematically determine for each patient the neocortical foci that are highly correlated and anticorrelated to the epileptogenic MTL by using a population-based map of normal resting-state MTL connectivity as a seed network of interest. This will allow us to selectively identify regions of relevant correlation to the MTL that fall within easily accessible areas for rTMS based on our technical experience (including most of the frontal, parietal, and lateral temporal cortex, while avoiding the frontopolar and occipital regions due to head positioning and the need for eyeglasses worn to calibrate the TMS neuronavigation system).

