We expect to downmodulate the excitability of the epileptogenic MTL, thus reducing seizure and IED frequency. Although it is difficult to predict the magnitude of such an effect given the unique nature of our targeting based on connectivity findings, prior rTMS studies in epilepsy have shown seizure frequency reductions in the 53-80% range, durable over at least eight weeks of follow-up, and IED frequency reductions in the 14-66% range.^{4,5} Our use of EEG recordings immediately pre- and post-rTMS, as well as at the end of the follow-up period, will allow for an estimation of immediate and delayed/durable effects on the epileptic state in these patients. We expect our results to prove the principle that patients with deep seizure foci can be safely treated by targeting accessible cortical regions and to provide guidance on which active rTMS protocol (high- or low-frequency) is optimal for MTLE.

Our analysis following the second rTMS protocol, in those subjects who participate in that portion of the study, will provide further evidence of the relative efficacy of the two rTMS protocols in downmodulating cortical excitability.

Brain image acquisition

Anatomical and functional connectivity MR images will be acquired using a dedicated research 3.0-Tesla magnet (General Electric Signa VH/i, GE Healthcare, Waukesha, WI) with a commercial head coil. Highresolution structural whole-brain images will be acquired using a T1-weighted sequence with 128 slices per slab, a 256 x 256 matrix, a field of view (FOV) of 256 mm, a slice thickness of 1.33 mm with 0.63 mm interslice gap, repetition time (TR) of 2530 ms, inversion time of 1100 ms, echo time (TE) of 3.39 ms, and flip angle of 7 degrees. Resting-state functional image acquisition will be performed while subjects are asked to rest quietly (acquisition time 6.4 min), using an echo-planar sequence sensitive to BOLD contrast with TR 6000 ms, TE 30 ms, FOV 256 mm, voxel size 2.0 x 2.0 x 2.0 mm, and flip angle 90 degrees.

Functional connectivity analysis

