All subjects will be between 18 and 64 years old and have a diagnosis of MTLE based on the combination of clinical semiology, neuroimaging findings, and EEG results. Subjects with ≥ 1 seizure with loss of awareness per 4-week period, on average, despite the use of antiepileptic drugs (AEDs), will be eligible. AEDs will not be adjusted during the study period, except in compelling clinical circumstances. Exclusion criteria are: 1) prior brain surgery or exposure to TMS; 2) rapidly progressive brain lesions (but low-grade gliomas, cystic lesions, mesial temporal sclerosis, or other static or slowly progressive lesions would be eligible); and 3) inability to tolerate MRI or TMS, or

specific MRI or TMS contraindication as set forth in standard protocols of our institution. Women of childbearing potential will be asked if they may be pregnant, questioned about the use of contraceptives if they are sexually active, and asked to identify the date of their last menstrual period. If investigators deem necessary, urine pregnancy testing may be performed before enrollment in the study.

The planned enrollment demographics for our study are derived from the demographic representation of the Greater Boston area (U.S. Bureau of the Census, 2000), from which the majority of our human subjects will be drawn. We thus expect to enroll approximately 10% Hispanic or Latino subjects and 90% non-Hispanic/Latino. Among racial categories, we expect to enroll approximately 75% white subjects, 10% black or African-American, and <5% each American Indian/Alaska native, Asian, and Native Hawaiian or Other Pacific Islander. No sex/gender or racial/ethnic groups will be excluded from this study.

Our subject selection criteria are based purely on age (18-64); diagnosis of MTLE; and nonfulfillment of specific exclusion criteria. MTLE appears to be evenly distributed across racial/ethnic lines. One of our exclusion criteria is pregnancy (due to lack of definitive information on fetal safety in MRI), but we do not believe this will independently affect the sex/gender composition of our enrolled subjects in any significant way.

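### Using the baseline diary as a covariate would make the primary seizure-frequency analysis more efficient than the planned Group by Time ANOVA, for a change of wording only

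*Combined protocol and SAP*

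**What the plan says.** The model is given once, in B3.B Statistical Considerations under Sample Size Justification. The sentence opens "Our expected statistical analyses will be based on intention to treat and will include an analysis of variance (ANOVA", and the model has "factors Group (low-frequency vs. high-frequency vs. sham) and Time (baseline vs. follow-up) with repeated measures on time, to assess both seizure frequency". Nowhere do the documents name a baseline covariate, a transformation, a percent-change endpoint or a count model.

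The endpoint wording does not settle the scale: "the primary outcome measure will be seizure frequency compared to baseline" (B3.A Overall Study Design, repeated under Data Analysis).

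The expected effect is relative. The sample-size paragraph says "we estimate the effect size of a potential decrease in mean seizure frequency at 56" percent, and Data Analysis adds that "prior rTMS studies in epilepsy have shown seizure frequency reductions in the 53-80% range".

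Both measurements are 12-week diaries (B3.A, items 2 and 6): "Subjects will keep a baseline seizure diary for 12 weeks" and "Subjects will keep a follow-up seizure diary for 12 weeks post rTMS". Entry has a floor and no stated ceiling: "Subjects with ≥ 1 seizure with loss of awareness per 4-week period, on average" (B3.C Subject Selection).

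**The concern.** With one baseline and one follow-up value per subject, the only term that compares change between groups is Group by Time, and that is an unadjusted comparison of absolute change. It subtracts the whole baseline value, as if each extra baseline seizure predicted exactly one extra follow-up seizure. A 12-week count is a noisy measure of a subject's underlying rate, so the true slope is below 1. A relative effect lowers it further in the active arms.

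The stake is power, not validity. With 10 subjects per arm there is little to spare, and the covariate is already being collected from every subject.

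**Working it through.** **1. The plan's own figure.** The stated total of 27 is reproduced if 56% is read as Cohen's f = 0.56 and entered in the G*Power repeated-measures, between-factors option with two measurements and a correlation of 0.5. Both settings are inferred; the document states neither.

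λ = f²·N·m / (1 + (m−1)ρ) = 0.3136 × 27 × 2 / 1.5 = 11.29, with 2 and 24 df, gives power 0.813. N = 24 gives 0.754.

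That option tests the Group effect averaged over both times, not the interaction. Its noncentrality, f²N/0.75, equals that of an ANCOVA with r = 0.5 (1 − 0.5² = 0.75).

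**2. What the planned test is.** On a trial data set of 3 × 10 subjects, the Group by Time F and the one-way F on follow-up minus baseline were both 1.6835. They are the same test.

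**3. Analytic comparison.** Assume equal variances, baseline/follow-up correlation r, f = 0.56 on the follow-up value and N = 30, so f²N = 9.408.
- Change score: λ = 9.408 / (2(1−r)), 2 and 27 df.
- ANCOVA: λ = 9.408 / (1−r²), 2 and 26 df.
- Error variance ratio: 2(1−r)/(1−r²) = 2/(1+r).

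| r | λ change | power | λ ANCOVA | power | variance ratio |
|---|---|---|---|---|---|
| 0.3 | 6.72 | 0.585 | 10.34 | 0.780 | 1.54 |
| 0.5 | 9.41 | 0.740 | 12.54 | 0.858 | 1.33 |
| 0.6 | 11.76 | 0.835 | 14.70 | 0.909 | 1.25 |
| 0.7 | 15.68 | 0.928 | 18.45 | 0.961 | 1.18 |
| 0.8 | 23.52 | 0.989 | 26.13 | 0.994 | 1.11 |

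ANCOVA gains throughout the table, but the gain falls from about 20 points at r = 0.3 to 0.5 points at r = 0.8.

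**4. Simulation under a relative effect.** From the documents: 10 per arm, 12-week counts at both times, entry floor of 1 per 4 weeks, 56% reduction (rate × 0.44) in both active arms. Assumed: lognormal true rates with median 4 per 4 weeks before the floor is applied, mean-1 lognormal period noise, Poisson counts, unchanged sham. Spread and noise are log SDs.

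| Spread / noise | ANOVA as written | Untransformed ANCOVA | Log ANCOVA |
|---|---|---|---|
| 0.6 / 0.3 | about 52% | 83% | 83% |
| 0.9 / 0.5 | about 23% | 46% | 57% |
| 1.2 / 0.7 | about 10% | 21% | 38% |

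The gain exceeds that in step 3 because a relative effect itself lowers the slope. Even without noise, the slope averaged over arms would be (0.44 + 0.44 + 1)/3 = 0.63, not 1. In these three settings the ANOVA as written needs about 22 per arm to match untransformed ANCOVA at 10.

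**5. How general.** Over 142 non-null settings (including sham improvement, dropout, one effective arm, additive effects, gamma rates, and benefit only in high-rate subjects), untransformed ANCOVA was never below the ANOVA as written. On a separate grid it was higher in 108 of 108. For the three settings of step 4 in order, power as written against untransformed ANCOVA was:
- sham also −20%: 25 vs 55%, 12 vs 26%, 6 vs 13%
- 15% random dropout: 44 vs 74%, 20 vs 38%, 9 vs 18%

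Type I error over 48 null settings was 2.4–5.3% as written and 2.8–5.1% for untransformed ANCOVA.

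**6. The log step.** Log ANCOVA beat untransformed ANCOVA in 101 of the 108 settings. It fell about 5 points short at low rates with little spread (75.8 vs 80.8% at median 2, spread 0.3, noise 0.3). With additive effects and uniform or normal rates, it was below even the ANOVA as written in 6 of 12 settings, by 1.5 to 11 points.

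**The case against.** **The reading is inferred.** The analyses are described as expected, the interaction is not named as the primary test, and silence about scale is not a commitment to raw frequencies. This stands, and it is why the point concerns the natural reading only. It also argues for writing the covariate and scale down before data are seen.

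**The planned test may have ample power.** A reader might infer from the table in step 4 that the ANOVA as written cannot reach the stated 80%. The documents do not support that, because they give no SD and no correlation. At period noise 0.2 it reached 89% (median 8, spread 0.3), 95% (median 15, spread 0.3) and 85% (median 15, spread 0.6). At the top of the plan's cited range, an 80% reduction, it reached 80% even at median 4, spread 0.6, noise 0.3. In step 3 it passes 80% once r is about 0.6.

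**Untransformed ANCOVA has its own misfit.** If the effect is relative, the follow-up slope in the active arms is about 0.44 of the sham slope, so one common slope is wrong and the group difference depends on baseline. This stands. The adjusted difference should be read at the mean baseline.

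**The baseline diary follows randomization.** True, since randomization occurs at consent. But the diary precedes stimulation and subjects are blinded, so it is still a pre-treatment covariate. The planned change score uses the same diary.

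**Conclusion.** The concern holds as one of efficiency, and it is a cheap improvement. The planned comparison is valid. Adjusting for the baseline diary gave equal or higher power in every setting simulated, with type I error at or close to the nominal 5% or below it. The direction is secure; the size is not. At the assumed median of 4 per 4 weeks the gain was about 31, 23 and 11 points in the three settings (83−52, 46−23, 21−10). It shrinks to almost nothing on a near-normal scale when r is about 0.8 or more.

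Two further inferences should be resisted. One is that the relative effect obliges the plan to make a log-scale analysis primary. That step usually adds power when rates are widely spread, but it leaves the plan's target of mean frequency, needs an arbitrary constant for zero counts, and can lose power as step 6 shows. It is a trade-off for the sponsor. The other is that adjustment makes 30 subjects enough: at 0.9/0.5 and 1.2/0.7 neither ANCOVA comes near 80%.

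IED frequency was not simulated and is not covered.

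**What to change.** - **Primary:** ANCOVA of the 12-week follow-up seizure rate on Group, with the 12-week baseline rate as covariate. Report adjusted differences versus sham with 95% confidence intervals, read at the mean baseline. This keeps the mean-frequency scale.
- **Supporting, prespecified:** either an ANCOVA of log(rate + a fixed constant) on Group and the log baseline formed the same way, or a count model with log baseline as covariate. With the log version, fix the constant in advance (1/3 per 4 weeks was used here, that is, one seizure per 12 weeks). State that the result approximates a geometric-mean ratio, not a ratio of mean frequencies; in simulation a true ratio of 0.44 gave median estimates of 0.47–0.49.

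**Cost:** SAP wording only, since both diaries are already planned. The primary change uses one error degree of freedom and assumes a common slope, which should be acknowledged in the text. No new visits, data or subjects are needed.

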The overall goal of this study is to open up the promising treatment of repetitive transcranial magnetic stimulation (rTMS), which has been shown to be effective against seizures in patients with surface neocortical foci, to a much larger population of patients with mesial temporal lobe epilepsy (MTLE) and other forms of epilepsy with deep foci, who are not currently considered good rTMS candidates. We plan to recruit thirty subjects with MTLE from our Comprehensive Epilepsy Center and through referrals from other clinicians. Subjects will undergo a series of noninvasive investigations, including high-resolution brain MRI, EEG, and rTMS. We plan to obtain blood oxygenation level-dependent (BOLD) functional magnetic resonance (MR) images in 30 patients with refractory MTLE during the task-free resting state. We will create a map for each patient of selected neocortical foci that are highly correlated and anti-correlated to the epileptogenic MTL by using a population-based map of normal resting-state MTL connectivity as a seed network of interest. We will conduct a controlled assessment of two different rTMS protocols applied to specific cortical targets (derived from connectivity imaging results) in the 30 patients with medically refractory MTLE. We will randomize subjects into three treatment groups: In Group 1, we will target low-frequency rTMS to cortical regions that are highly correlated with the epileptogenic MTL. In Group 2, we will target high-frequency rTMS to cortical regions that are highly anti-correlated with the epileptogenic MTL. Group 3 will receive sham rTMS as a control intervention. At 12-week follow-up, outcome measures will be seizure frequency (primary) and interictal epileptiform discharge (IED) frequency (secondary). All subjects will have EEG recordings prior to the first TMS session, after the last session, and at 12-week follow-up. Subjects will be blinded to their treatment group assignment. Subjects and family members or caregivers will be asked to maintain diaries of all seizures and possible adverse effects, which will be reviewed by an investigator blinded to treatment group assignments. For each subject, the MRI will be performed in one 1-hour session on one day, the EEGs will be performed in three 1-hour session on three separate days (pre-rTMS, post-rTMS and 12 weeks after rTMS) and rTMS will occur over ten daily 30-minute sessions.

Overall Study Design

Subject Enrollment

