Stimulation will be performed with a Nexstim eXimia TMS stimulator with real-time MRI neuronavigation (Nexstim NBS software version 3.2.1, Nexstim Ltd, Helsinki, Finland) and a figure-of-eight coil (mean diameter 59 mm, outer diameter 70 mm). Resting motor threshold (RMT) will be determined via surface electromyography recorded using pre-gelled disposable Ag/AgCl electrodes, with the active electrode over the first dorsal interosseus (FDI) muscle, the reference electrode over the metacarpophalangeal joint, and the ground electrode over the wrist. RMT will be conventionally defined as the minimum stimulus intensity that elicits a motor evoked potential of at least 50 μ V in at least five out of ten trials. Low-frequency rTMS will employ a 1-Hz, 95% RMT protocol for 30-minute sessions delivered once each day over ten consecutive weekdays. High-frequency rTMS will employ a 10-Hz, 110% RMT protocol delivered similarly over ten days. Sham TMS will employ a specially fabricated coil that provides no magnetic stimulation but has a similar appearance and creates an auditory artifact that mimics TMS, and will be targeted toward a highly correlated cortical target.

EEG analysis

EEG will be recorded using a 60-channel TMS-compatible system (eXimia EEG, Nexstim Ltd, Helsinki, Finland). EEG signals will be referenced to an additional electrode on the forehead, filtered (0.1 – 500 Hz) and sampled at 1450 Hz with 16-bit resolution. Two extra sensors will be used to record electrooculogram, and electrode impedance will be kept below 5 k Ω at all times. All recordings will be at least 60 minutes in duration, and subjects will be kept awake to control for the effects of

sleep on IED frequency. Each EEG recording will be inspected visually and IEDs will be counted for the total duration of the artifact-free EEG by an investigator board-certified in clinical neurophysiology and blinded to subjects' treatment group assignments.

B. Statistical Considerations

Sample Size Justification:

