We expect to demonstrate pathological connectivity involving the MTL and specific cortical regions; this will be a major step in understanding MTLE pathogenesis and in defining targets for stimulation. We will use an in-house functional connectivity software toolbox for analysis, as we have done for our Preliminary Data. Briefly, our steps include realigning, normalizing, and coregistering functional images, followed by segmentation and BOLD signal extraction. Band-pass filtering and smoothing will be applied, and possible confounders removed. A population-based map of MTL connectivity (derived from normal individuals), with rTMS-accessible regions removed, will be used as a seed network to create color-coded functional connectivity maps identifying rTMS-accessible areas of significant correlation and anti-correlation to the average BOLD time-series within the MTL network,

subject to a voxel-wise statistical threshold and cluster thresholding.

We will then conduct a controlled assessment of two different rTMS protocols applied to specific cortical targets (derived from connectivity imaging results) in the 30 patients with medically refractory MTLE. The cohort will be randomized into three treatment groups. In Group 1, we will target continuous low frequency rTMS (1 Hz, at 95% resting motor threshold (RMT), over ten daily 30-minute sessions) to cortical regions that are highly correlated with the epileptogenic MTL. In Group 2, we will target high-frequency rTMS (10 Hz, 110% RMT, 10 daily sessions) to cortical regions that are highly anti-correlated with the epileptogenic MTL. Group 3 will receive sham TMS as a control intervention (using a sham coil over a highly correlated cortical region). At 12-week follow-up, the primary outcome measure will be seizure frequency compared to baseline, and the secondary outcome measure will be IED frequency compared to baseline. Subjects will be blinded to their group assignment, as will the investigator who reviews seizure diaries and determines IED frequency on EEG. Adverse events will be tracked closely throughout the study protocol.

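### The EEG taken after the last rTMS session has no place in the stated IED model, and no comparison with sham is prespecified for the immediate effect

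*Combined protocol and SAP*

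**What the plan says.** **Schedule.** Section B3.A, Overview: "All subjects will have EEG recordings prior to the first TMS session, after the last session, and at 12-week follow-up". Under Overall Study Design, steps 3, 5 and 7 are the pre-rTMS, post-rTMS and final EEGs. Step 5 reads: "EEG recording of interictal epileptiform discharge (IED) frequency will occur after the last TMS session". Under EEG analysis, every recording is read by a blinded investigator: "Each EEG recording will be inspected visually and IEDs will be counted for the total duration of the artifact-free EEG".

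**Purpose.** Section B3.B, Data Analysis, says that the recordings just before and just after rTMS, together with the one at the end of follow-up, "will allow for an estimation of immediate and delayed/durable effects on the epileptic state in these patients".

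**Outcome definition.** At the 12-week follow-up, "the secondary outcome measure will be IED frequency compared to baseline" (B3.A, Overall Study Design, and again in B3.B, Data Analysis).

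**Model.** Section B3.B, Sample Size Justification, opens: "Our expected statistical analyses will be based on intention to treat and will include an analysis of variance (ANOVA". The between-subject factor has three levels, one for each treatment arm. The within-subject factor is given as "Time (baseline vs. follow-up) with repeated measures on time, to assess both seizure frequency (primary outcome) and IED frequency (secondary outcome". Bonferroni-corrected post hoc analyses may follow if indicated. No contrasts are named.

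**The concern.** One two-level Time factor serves both outcomes. Seizure frequency has two diary periods, so it fits. IED frequency has three recordings, and because the secondary outcome is defined at 12 weeks, the follow-up level cannot be read as the recording after the last session. That recording is therefore outside the one model the plan names.

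The Data Analysis section nevertheless presents immediate and durable effects as something the trial will estimate. For the immediate effect it gives no model, comparison group or multiplicity rule. Two consequences follow. An analysis chosen after the data are seen would be exploratory, whatever it showed. The report would also have two candidate IED results, immediate and week 12, with no rule on which leads. The documents support a gap in prespecification, and no more than that.

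**Working it through.** **1. The plan's own figure.** The total of 27 comes from seizure frequency. It can be reproduced with the noncentral F test for the Group effect, where lambda = N f² m / [1 + (m − 1) rho] and df = (k − 1, N − k). Inputs are k = 3 groups, m = 2 time levels, f = 0.56 and rho = 0.5. Reading the stated 56% as f, and the value of rho, are assumptions. N = 24 gives power 0.754 and N = 27 gives 0.813, so 27 is the smallest multiple of three that reaches 80%. This agrees with a two-level Time factor but does not prove it, because rho is not stated. Nothing below changes this figure.

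**2. Recordings inside and outside the model.**
- Planned in the first phase: 30 subjects x 3 EEGs = 90.
- Entering the two-level IED model: 30 x 2 = 60.
- Outside it: 90 − 60 = 30, or one third. All 30 are the recordings after the last session.

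Repeat EEGs in subjects invited back for a second protocol are not counted.

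**3. What the stated model tests.** With two time levels, the Group x Time test is a comparison of change scores (week 12 minus baseline) between groups. Its error df at N = 30 is 30 − 3 = 27. The immediate recording does not enter it.

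**4. Precision at week 12 with and without baseline adjustment.** Assume unit variance at each recording and correlation rho between recordings. The documents give no value for rho.
- Change score, as in the plan: 2(1 − rho).
- Baseline as covariate: 1 − rho².
- Ratio: (1 − rho²) / [2(1 − rho)] = (1 + rho)/2.

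| rho (assumed) | Change score | Baseline-adjusted | Reduction |
|---|---|---|---|
| 0.4 | 1.20 | 0.84 | 30% |
| 0.6 | 0.80 | 0.64 | 20% |
| 0.8 | 0.40 | 0.36 | 10% |

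The covariate costs one error df (27 to 26), so the realised gain in a trial of this size is slightly smaller. With complete data, the gain at week 12 comes from the baseline covariate and not from the third EEG. What the third EEG adds is the immediate contrast.

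**5. Multiplicity.** Two tests at 0.05, one per visit, would have a joint error rate of 1 − 0.95² = 0.0975 if independent. Bonferroni gives 0.05/2 = 0.025 each. With two active arms against sham at both visits there are four contrasts, and 0.05/4 = 0.0125 each.

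**The case against.** The strongest reply is that the model fits the declared secondary outcome. IED frequency is defined at 12 weeks against baseline, and a two-level factor answers exactly that. The Data Analysis section promises an estimate of the immediate effect, not a test, in a paragraph of expectations. This stands: the declared secondary comparison is covered, and only a further time point of a secondary outcome is affected. It does not close the gap, since an estimate the trial says it will deliver still needs a stated comparison.

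A reader might infer that the recording after the last session goes unused, or that the immediate effect will never be tested. The documents do not support either. Every EEG is read and counted, the Data Analysis section assigns this recording a purpose, and the list of analyses is open-ended. The accurate statement is that nothing is prespecified. The open wording and the conditional post hoc tests permit an immediate analysis, but they specify none, and the ANOVA they follow does not contain that time point.

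A reader might also claim a larger precision gain by averaging the two post-baseline EEGs. That is a different analysis. It would merge the immediate and durable effects that the plan wants to separate, and it would dilute an effect present at only one visit.

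Finally, a third Time level or two named change contrasts would be enough to close the gap. That is true. Baseline adjustment goes further, and is justified by the gain shown in step 4.

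**Conclusion.** The concern holds as a gap between the stated aim and the stated analysis. Thirty of 90 first-phase EEGs lie outside the only named IED model, and the immediate effect has no prespecified comparison with sham. These counts come directly from the documents and need no assumption beyond full enrolment and complete recordings.

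The precision gain at week 12 is conditional. It is 20% lower variance at an assumed correlation of 0.6, and 30% to 10% over 0.4 to 0.8, with equal variances on the analysis scale.

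The reach is limited to the secondary outcome. The primary outcome, the stated requirement of 27 and the planned enrolment of 30 do not change. The documents give no separate size for an immediate IED effect, so nothing can be said about how strong that signal would be.

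**What to change.** For IED frequency only, replace the two-level ANOVA with a repeated-measures mixed model:

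- two post-baseline visits (immediate, week 12), Group, Visit and Group x Visit;
- the pre-rTMS IED rate as covariate, with its coefficient allowed to differ by visit, and unstructured covariance between the two visits;
- an outcome scale that admits recordings with no IEDs, since the log of a zero rate is undefined. Options are a transformation defined at zero, or a count model with artifact-free recording time as offset;
- week 12, each active arm against sham, kept as the secondary test;
- the immediate contrast against sham named, and either labelled supportive or included in the Bonferroni correction.

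The seizure-frequency analysis can stay as it is for this purpose.

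The cost is one paragraph in the Statistical Considerations section. No visits, recordings or subjects are added, because all three EEGs are already scheduled. If the immediate contrasts join the Bonferroni family, the per-test level for week 12 falls (from 0.025 to 0.0125 with two active arms). Labelling them supportive avoids that.
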